4.3 Patient Withdrawal Criteria

Patients may be removed from the study for reasons including the following:

1. Significant protocol violation on the part of the Investigator or patient;
2. Significant noncompliance on the part of the patient as determined by the Investigator in consultation with the Medical Monitor;
3. Patient withdraws consent;
4. During the study, patient has the need for medications, supplements, ingredients and herbal therapies that are excluded (see [Section 7.4](#), "Prohibited Medications" for examples in each category; this list is not all inclusive);
5. Unacceptable toxicity based on laboratory or other clinical findings, based on PI opinion;

6. Occurrence of any adverse event (AE) or condition that could, in the Investigator's opinion, interfere with the evaluation of the treatment effect or put the patient at undue risk;
7. Pregnancy; or
8. Other criteria, at the Investigator's discretion in consultation with the Medical Monitor.

5 STUDY TREATMENTS

5.1 Identity of Investigational Product

The investigational product for the open-label crossover study treatment will be DST-0509 supplied in 360 mg, 180 mg and 90 mg film coated tablets supplied by DisperSol Technologies, LLC ([name]; see Investigator's Brochure [9]).

The methods used in, and the facilities and controls used for the manufacturing, processing, packaging, and holding of this drug substance conform with Current Good Manufacturing Practices (cGMP) in accordance with 21 CFR Parts 210 and 211. DisperSol will maintain certificates of analysis for each ingredient, documenting its purity and potency.

The following will be printed on the bottle label: Study ID, Lot/Batch No., placeholders for Site No., Screen No., Patient Initials and Date Dispensed.

Jadenu is commercially available as tablets, and Exjade as tablets for suspension, and both will be ordered by prescription and provided by the patient. Dosing will be at equivalent (mg for mg) doses of DST-0509 or Jadenu. If converting from Exjade to DST-0509, the dose will be scaled for each treatment by 28 mg/40 mg (DST-0509/Exjade).

5.2 Investigational Product Storage and Accountability

Investigational product will be stored at room temperature in a locked area with limited access.

Investigational product will be shipped to the study site. The Principal Investigator or designee will inventory and acknowledge receipt of all shipments of investigational product. The Principal Investigator or designee must keep accurate records of investigational product via the master investigational product accountability logs and the patient investigational product accountability logs. Supplies of investigational product will be checked and accountability records will be reviewed by the Clinical Research Associate (CRA) at monitoring visits. The completed accountability logs will be collected by the CRA at the close of the study. At the end of the study, all unused, partially used, empty or unopened kits or bottles will be returned to DisperSol or its designee for destruction. A written explanation will be required for any missing product.

Investigational supplies are to be used only in accordance with this protocol and under supervision of the Principal Investigator. All records must be available for inspection by Accelovance, Inc. and DisperSol personnel or their designees, and are subject to inspections by the regulatory authorities at any time.

5.3 Methods of Assigning Patients to Treatment Groups

Each clinical site will be assigned a unique 2-digit number. At each clinical site, a unique 3-digit screening number will be assigned to each patient after written IC is obtained. Patient screening numbers will be assigned sequentially at the site. Each patient will have a unique identifier that combines both the site and screening number. At Visit 3 (Day 1), a randomization number will be assigned centrally (by Accelovance, Inc. or by Interactive Voice Response System [IVRS], in accordance with the investigational product manufacturer) to each patient in a sequential manner as they become eligible for randomization. The randomization number will correspond to a predetermined treatment. Screening and randomization numbers must not be re-used once assigned, even if the patient does not take the investigational product.

Subjects who were taking Exjade prior to study start will receive Exjade at their prescribed dose during the study and those taking Jadenu at study start will receive Jadenu at their prescribed dose.

5.4 Administration of Investigational Product

DST-0509 will be supplied in 360 mg, 180 mg and 90 mg tablets. Jadenu is commercially available as tablets and Exjade as tablets for oral suspension and will be provided by the patient with their ongoing prescription. Dosing will be at equivalent (mg for mg) doses of DST-0509 or Jadenu. If converting from Exjade, the dose will be scaled for each treatment by 28 mg/40 mg (treatment/Exjade).

This is an open-label crossover study. Patients will receive Exjade or Jadenu at their previous stable dose. DST-0509 is taken with food, Jadenu is taken with or without a light meal, and Exjade is recommended to be taken without food. However, either Jadenu or Exjade can be administered according to the patient's previous regimen.

Each subject will be provided with sufficient DST-0509 for the respective treatment period and site staff will ensure prescription for Jaden and Exjade are sufficient for the respective treatment periods. The first dose will be taken at Visit 3 (Day 1) and the final dose will be taken at Visit 10 (Day 63).

5.5 Treatment Accountability and Compliance

At clinic visits, dosing will be observed by site staff. Accountability of investigational product consumption between visits will be evaluated by site staff through patient interview and the

counting of investigational product at Visits 3 through 10 (Days 1 through 63). The patient will be asked to bring the used and unused containers to each visit.

Lost or discarded investigational product should not be included in the calculation. Compliance will be determined at the Investigator's discretion but is recommended to be defined as 100% consumption of the scheduled intakes of investigational products. Dosing instructions are provided at Visit 3 (Day 1) and Visit 7 (Day 36); however, further counseling will be provided when compliance is unacceptable.

5.6 Blinding and Unblinding Method

Not applicable: this is an open-label study.

6 SCHEDULE OF PROCEDURES AND ASSESSMENTS

Table 6-1 represents the procedures and assessments at each of the scheduled visits. Details of each visit are provided in [Section 6.1](#) through [Section 6.5](#).

Table 6-1. SCHEDULE OF PROCEDURES

Period	Screening	Eligibility	7-day Washout ¹	Period 1 Treatment (DST-0509 or Jadenu/Exjade)				7-day Washout	Period 2 Treatment (Jadenu/Exjade or DST-0509)				7-day Washout ¹¹ and Follow-up
				3	4	5	6		7	8	9	10/ET	
Visit	1	2		3	4	5	6		7	8	9	10/ET	11
Day	-28 to -15	-14 to -8	-7 to -1	1	7	14	28	29-35	36	42	49	63	70
Window (days)					±1	±1	±1		±1	±1	±1	±1	±1
Informed Consent	X												
Medical and Surgical History	X												
Prior Medications	X												
Body weight and Height	X												
Washout Instructions ²		X					X					X	
Eligibility Review	X	X		X									
Randomization				X									
Dispense Investigational Product ³				X					X				
Safety													
Vital signs ⁴	X			X		X	X		X		X	X	
Physical Examination ⁵	X			X		X	X		X		X	X	
Electrocardiogram (ECG)				X					X				
Chemistry, Hematology (CBC) and Urinalysis ⁶	X			X		X	X		X		X	X	
Serum CRP	X	X		X			X		X			X	
Urine Pregnancy Test ⁷	X												
Urine for Protein:Creatinine	X			X		X	X		X		X	X	
ECOG PS (Appendix C)	X			X			X		X			X	
Adverse Events				X	X	X	X		X	X	X	X	X
Concomitant Medications	X			X	X	X	X		X	X	X	X	X
Dispense gastrointestinal AESI diary and Bristol Stool Chart	X			X					X				

Period	Screening	Eligibility	7-day Washout ¹	Period 1 Treatment (DST-0509 or Jadenu/Exjade)				7-day Washout	Period 2 Treatment (Jadenu/Exjade or DST-0509)				7-day Washout ¹¹ and Follow-up
				3	4	5	6		7	8	9	10/ET	
Visit	1	2		3	4	5	6		7	8	9	10/ET	11
Day	-28 to -15	-14 to -8	-7 to -1	1	7	14	28	29-35	36	42	49	63	70
Window (days)					±1	±1	±1		±1	±1	±1	±1	±1
and diary													
Review gastrointestinal AESI diary		X		X	X	X	X		X	X	X	X	
Review Bristol Stool Chart diary		X		X	X	X	X		X	X	X	X	
Collect gastrointestinal AESI diary				X			X					X	
Collect Bristol Stool Chart diary				X			X					X	
Treatment Compliance ⁸				X	X	X	X		X	X	X	X	
Administer SICT questionnaire ⁸		X											
Efficacy Assessments													
Ferritin monitoring	X	X		X			X		X			X	
Pharmacogenetic monitoring		X											
Pharmacokinetics													
Trough sampling ⁹	X	X											
Pharmacokinetic sampling ⁹				X	X		X		X	X		X	
Next Visit Instructions ¹⁰				X	X	X	X		X	X	X		

Abbreviations AESI = adverse events of special interest; CBC = complete blood count; CRP = C-reactive protein; ECOG PS = Eastern Cooperative Oncology Group Performance Status; SICT = satisfaction with iron chelating therapy; ET = Early Termination.

1. Instructions for washout provided at Eligibility visit (Visit 2).
2. For patients on iron chelation therapy prior to randomization, and for washout for all patients between periods and after last treatment.
3. DST-0509 will be supplied in 360 mg, 180 mg and 90 mg tablets. Patients will receive Jadenu or Exjade at their previous stable dose. All treatments will be administered daily orally with food in the morning. Dosing will be at equivalent (mg for mg) doses of DST-0509 for Jadenu. If crossing over from Exjade to DST-0509, or vice versa, the dose will be scaled to 28 mg/40 mg (DST-0509/Exjade).
4. Vital signs will include the measurement of blood pressure, heart rate, respiratory rate and body temperature.
5. A full physical examination will be performed at Screening, Day 28 and Day 63. A brief physical examination will be performed on Day 1, 14, 36, and 49.

6. Chemistry, Hematology (CBC) and Urinalysis measurements are described in Section 7.11.1.
7. Urine Pregnancy Test will be performed for women of childbearing potential.
8. At clinic visits, dosing will be observed by site staff. Initial and returned pill counts will be used to calculate compliance (% doses taken per protocol). Additional measures of compliance will include Investigator enquiry into patient prescription refill records if available, satisfaction with iron chelation therapy (SICT) questionnaire [ref 8; Appendix D] and use of patient diaries.
9. A trough sample will be collected at Visit 1 and Visit 2. Blood samples for pharmacokinetic sampling will be drawn predose (-0.5 hour for trough levels) and at 1, 2, 4, and 8 hours post dose on Days 1, 7, 28, 36, 42 and 63. The allowed sampling “window” is ± 15 min before 4 hours and ± 30 min at 4 hours respectively. For the 8-hour time point the allowable sampling window is ± 1 hour. A 7-day washout period will occur at the end of study on Day 63; completion confirmed by a follow-up phone call on Day 71 to inquire on adverse events and concomitant medications.
10. Patients are instructed not take their medication on the morning before they arrive for their next visit.
11. A 7-day washout period will occur at the end of study on Day 63; completion confirmed by a follow-up phone call on Day 70 to inquire on adverse events and concomitant medications.

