STUDY DESIGN AND DURATION:	

This is a multi-center, open-label, two-period cross-over, patient-pilot study comparing DST-0509 to patient's prior ICT (Exjade or Jadenu) administered orally once daily (QD) for 28-days in each period, with a 7-day washout before the first treatment period, between treatment periods, and at the end of the study before patients recommence their prescription regimens (see Table 6-1). Patients will be randomized to one of two treatment sequences: DST-0509→Exjade/Jadenu or Exjade/Jadenu→DST-0509 (with subjects who were taking Exjade prior to study start receiving Exjade and those taking Jadenu at study start receiving Jadenu). This study is designed to assess the safety, tolerability, evidence of iron chelating activity, and PK profile of DST-0509 compared to Jadenu or Exjade in inadequately responding patients. Inadequate response to standard chelation therapy is defined based on the medical literature [6,7].

Up to 36 patients will be randomized 1:1 into one of two treatment sequences (study arms), of which up to 100% may be on Jadenu or Exjade at study entry, or a mix of the two. The planned randomization will assign up to 18 patients in each of two sequences: Sequence A: DST-0509 crossed to Exjade or Jadenu; Sequence B: Jadenu or Exjade crossed to DST-0509. The comparator treatment will be the patient's current chelation treatment. At the end of the study, patients previously on Jadenu or Exjade will revert to receiving their pre-study medication and dose following a 7-day washout period. A sufficient number of patients will be enrolled so there will be no need to replace study drop-outs. Study duration is approximately 14 weeks for each patient. A Study Flow Diagram is presented after this Synopsis (see Figure 3-1).

INCLUSION CRITERIA:

The following are the main inclusion criteria:

1. Written informed consent obtained prior to any study-related procedure being performed;
2. Patients at least 18 years of age or older at the time of consent;
3. Patient with TDT or NTDT syndromes and iron overload currently receiving iron chelation therapy with Jadenu or Exjade and demonstrating inadequate response assessed with serum ferritin and LIC;
4. Stable dosing with Jadenu or Exjade for >3 months prior to screening and receiving the maximal dose (Jadenu: 28 mg/kg or Exjade: 40 mg/kg);

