8. Other criteria, at the Investigator's discretion in consultation with the Medical Monitor.

DOSAGE FORMS AND ROUTE OF ADMINISTRATION:

DST-0509 will be supplied in 360 mg, 180 mg and 90 mg tablets. Jadenu is commercially available as tablets and Exjade as tablets for oral suspension and will be provided by the patient with their ongoing prescription. Dosing will be at equivalent (mg for mg) doses of DST-0509 or Jadenu. If converting from Exjade, the dose will be scaled for each treatment by 28 mg/40 mg (treatment/Exjade).

This is an open-label crossover study. Patients will receive Exjade or Jadenu at their previous stable dose. DST-0509 is taken with food, Jadenu is taken with or without a light meal, and Exjade is recommended to be taken without food. However, either Jadenu or Exjade can be administered according to the patient's previous regimen.

OUTCOME VARIABLES:

The primary outcome of the study will be the safety, overall tolerability, and preliminary evidence of DST-0509 iron chelating activity compared to Jadenu or Exjade.

Iron chelation

Serum ferritin will be assessed at screening (Visits 1 and 2) and on Days 1, 28, 36 and 63. Change from baseline in each treatment period will be assessed as the main efficacy variable for serum ferritin.

Efficacy responders, i.e., the proportion of patients who achieve serum ferritin <800 mcg/L, will be evaluated.

Pharmacokinetics

Trough deferasirox levels will be collected in the Screening period at approximately -4 and -2 weeks. Blood samples for PK analysis will be collected predose (-0.5 hour for trough level) and at 1, 2, 4, and 8 hours post dose on Days 1, 7, 28, 36, 42 and 63. The PK parameters of DST-0509 and Jadenu or Exjade will be derived from the concentration time data. The allowed sampling "window" is ± 15 min for the 1 and 2 hour time points, and ± 30 min for the 4 hour time point. For the 8 hour time point, the allowable window is ± 1 hour.

The goal of the PK analyses will be to characterize the PK of the inadequate responder population on their current DFX therapy at the end of 4 weeks compared to 4 weeks of therapy with DST-0509. The hypothesis is that a significant proportion of inadequate responders will have low exposures on current therapy compared to exposure with DST-0509.

Exploratory Pharmacogenomics

A blood sample will be taken at Visit 2 to collect germline DNA to allow for later exploratory sub-analyses of genotype vs exposures.

SAFETY AND TOLERABILITY ASSESSMENTS:

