2.2 Secondary

To determine the single and multiple dose pharmacokinetic (PK) profile of total deferasirox (iron-bound and unbound) plasma concentrations during DST-0509 and Jadenu or Exjade treatments in fed TDT and NTDT patients.

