6.3.1 Visit 3 (Day 1)

Procedures as identified in Table 6-1.

- Eligibility Review
- Randomization: subjects who were taking Exjade prior to study start will receive Exjade during the study and those taking Jadenu at study start will receive Jadenu.
- Dispense Investigational Product (see instructions in [Section 5.4](#))
- Vital signs (blood pressure, heart rate, respiratory rate and body temperature)
- Physical Examination (brief)
- 12-Lead electrocardiogram (ECG), predose/pre-sampling
- Chemistry, Hematology (CBC) and Urinalysis
- Serum CRP
- Urine for protein and creatinine
- ECOG PS (see [Appendix C](#))
- Adverse Events
- Concomitant Medications
- Collect gastrointestinal AESI diary and Bristol Stool Chart diary
- Review gastrointestinal AESI diary
- Review Bristol Stool Chart diary
- Dispense gastrointestinal AESI diary and Bristol Stool Chart and diary
- Treatment compliance
- Ferritin monitoring
- Pharmacokinetic sampling at predose (-0.5 hour) and 1, 2, 4, and 8 hours postdose
- Patients are instructed not to take study medication on the morning before they arrive for their next visit

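### Schedule footnote 3 and the fed-state PK objective conflict with Section 5.4, which lets Jadenu and Exjade follow a possibly fasted regimen; under Section 5.4 the exposure ratios are as-used, not fed-state

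*Protocol*

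**What the plan says.** Two sets of statements in the current protocol describe the food condition differently.

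**Fed for everything.** Footnote 3, attached to the dispensing row of the schedule in both the synopsis and Table 6-1, reads: "All treatments will be administered daily orally with food in the morning". The secondary objective (synopsis and Section 2.2) is the single- and multiple-dose PK profile "during DST-0509 and Jadenu or Exjade treatments in fed TDT and NTDT patients".

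**Fed for DST-0509 only.** Section 5.4, repeated in the synopsis under dosage forms and route of administration, takes the products one at a time: "DST-0509 is taken with food, Jadenu is taken with or without a light meal, and Exjade is recommended to be taken without food". It then adds that "either Jadenu or Exjade can be administered according to the patient's previous regimen".

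Four other places bear on which text governs:

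- The introduction to Section 6 says of the visits: "Details of each visit are provided in" Sections 6.1 to 6.5.
- The two dispensing visits (6.3.1, Day 1, and 6.4.1, Day 36) both list "Dispense Investigational Product (see instructions in" Section 5.4.
- The synopsis and Section 3.1 define the reference: "The comparator treatment will be the patient's current chelation treatment".
- The synopsis gives the PK goal as being to "characterize the PK of the inadequate responder population on their current DFX therapy" after 4 weeks and to compare this with 4 weeks of DST-0509.

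The comparison itself is in Section 8.5.4.2: an ANOVA on log-transformed Cmax and AUC with treatment, period, sequence and patient terms, reported as a ratio with a 90% confidence interval, separately for each reference product.

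**The concern.** A dosing instruction and a stated objective say one thing, and the administration section says another. Nothing in the protocol reconciles them, and each version appears in both the synopsis and the body, so this is not one stray typing error.

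A fasted previous regimen is realistic. The appended Exjade label (Appendix A, 2.3) directs dosing on an empty stomach, and the appended Jadenu label (Appendix B, 2.3) allows it. For such a patient, Section 5.4 permits a fasted comparator dose and footnote 3 forbids it.

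What is at stake is the meaning of the DST-0509/comparator ratio. If DST-0509 is always fed and the comparator sometimes fasted, food state changes together with treatment within that patient, and the model has no term that separates the two. The ratio is then a comparison of products as used, not the fed-state profile that the objective names. If some sites worked from footnote 3 and others from Section 5.4, the ratio would be neither cleanly.

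**Working it through.** **The plan's own figure.** The protocol gives no number for this point. Its only design calculation is the chance of seeing diarrhoea events (Section 8.1), and it reproduces. At a 12% rate and N = 30, P(at least 1) = 1 − 0.88^30 = 0.978 (stated 98%), and P(at least 2) = 0.890 (stated 89%). Neither depends on food state.

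**Where the texts collide.**

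| Previous regimen | Footnote 3 | Section 5.4 | Conflict? |
|---|---|---|---|
| Jadenu with a light meal | met | met | no |
| Jadenu on an empty stomach | breached | met | yes |
| Exjade on an empty stomach, per label | breached | met | yes |
| Exjade with food, by habit | met | permitted, though not the recommendation | no |

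The conflict is therefore confined to patients who take their comparator fasted. The documents do not give their share.

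**Size for Jadenu.** Inputs are from the healthy-volunteer food study in Sections 1.2 and 3.2: against fasting, a low-fat meal lowers AUC by 11% and Cmax by 16%. Let f be light-meal exposure divided by fasted exposure:

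- AUC: f = 1 − 0.11 = 0.89
- Cmax: f = 1 − 0.16 = 0.84

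DST-0509 is fed in both scenarios, so its own food effect cancels, and

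(DST-0509 fed / Jadenu fasted) = f × (DST-0509 fed / Jadenu light meal).

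If every Jadenu patient is fasted, the ratio is multiplied by 0.89 (AUC) and 0.84 (Cmax). If only a share p is fasted and the rest take a light meal, the geometric mean ratio is multiplied by f^p. The values of p below are assumptions:

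| p fasted | AUC factor | Cmax factor |
|---|---|---|
| 25% | 0.89^0.25 = 0.971 | 0.84^0.25 = 0.957 |
| 50% | 0.89^0.5 = 0.943 | 0.84^0.5 = 0.917 |
| 75% | 0.89^0.75 = 0.916 | 0.84^0.75 = 0.877 |
| 100% | 0.890 | 0.840 |

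All of these lower the DST-0509/Jadenu ratio.

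**Size for Exjade.** Section 1.1 and Appendix A, 12.3 say only that a meal raises AUC, by a varying amount. A fasted Exjade reference would therefore have lower exposure than a fed one, and the ratio would move in favour of DST-0509. No figure is given, so the shift cannot be computed. It stays within the Exjade analysis, because Section 8.5.4.2 does not pool the two references. The Exjade group may be small or empty, since the synopsis lets up to 100% of patients be on either product.

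**The case against.** The strongest reply is that the matter is largely settled in operation. Section 5.4 is the section on administration, it treats each product by name, and both dispensing visits send the site there. The comparator is defined as current treatment and the PK goal is exposure on current therapy. On that reading, what is left is an out-of-date footnote and one word in the objective. Most of this stands: the balance of the text does favour Section 5.4, and an as-used comparison is a legitimate choice. It does not remove the point, because footnote 3 hangs on the same dispensing row that the site uses, and Section 5.4 does not reliably deliver the fed objective for the comparators.

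Four stronger readings are tempting and are not supported:

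- *The two instructions can never both be followed.* They can for Jadenu with a light meal, and for any patient who already takes the comparator with food.
- *The food difference could hide a real advantage of DST-0509.* With an all-fasted Jadenu reference, a light-meal advantage below 1/0.89 = 1.12 (AUC) or 1/0.84 = 1.19 (Cmax) would come out at or below 1. But Section 8.5.4.2 attaches no margin, test or go/no-go rule to the ratio, so no decision turns on those values.
- *The Jadenu comparison could be biased towards DST-0509.* Factors of 1.18 (AUC) and 1.29 (Cmax) follow only if the undefined food in footnote 3 is taken as a high-fat meal, which Sections 1.2 and 3.2 advise against for Jadenu.
- *Food state on PK days will go unrecorded.* The visit lists do not mention it, but the case report form is not shown and may already collect it.

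The shift is also modest beside the pilot's imprecision. Assume a within-patient CV of 20% to 40% (not in the documents) and 30 completers on one reference (28 df, t = 1.701). The log-scale half-width is 1.701 × √(ln(1 + CV²)) × √(2/30), which is 0.087 to 0.169, or about 9% to 18%. At 25% to 50% fasted, the food shift is about 3% to 6% for AUC and 4% to 8% for Cmax. A shift of this kind is a bias, so imprecision does not cancel it, but the comparison puts it in proportion.

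**Conclusion.** The inconsistency is real. Footnote 3 and the fed objective cannot stand beside Section 5.4 for patients whose previous regimen is fasted. Read as the rest of the protocol suggests, Section 5.4 governs, and the Cmax and AUC ratios are as-used comparisons that may include a food difference.

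For Jadenu, the largest shift relative to a light-meal fed comparison is a factor of 0.89 (AUC) and 0.84 (Cmax), against DST-0509. It rests on the healthy-volunteer food effect carrying over to these patients and on every Jadenu patient being fasted; it shrinks with the true share, which is unknown. For Exjade, the direction favours DST-0509 and the size is unknown.

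The consequence is limited to interpreting a secondary PK objective in a pilot. The primary safety endpoints and the sample size are unaffected. This ranks between a minor correction and one that should be made.

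**What to change.** Choose one food condition and state it throughout.

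**Preferred: as-used.** Correct footnote 3 in the synopsis schedule and in Table 6-1 to match Section 5.4. Remove the fed condition for Jadenu and Exjade from the secondary objective in the synopsis and Section 2.2. Describe the exposure ratio as a comparison of DST-0509 with food against the comparator as the patient usually takes it. The cost is wording in four places. The drawback is that the ratio is not an effect of formulation alone.

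**If fed against fed is intended.** The synopsis dosing text, Section 5.4 and both copies of footnote 3 must all specify a defined light meal for every product and acknowledge the departure from the Exjade label. That is also four places. Some patients would have to change their usual regimen.

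**Optional under either choice.** Record fed or fasted state and meal type at the observed doses on Days 1, 7, 28, 36, 42 and 63, if the case report form does not already do so. Clinic doses are already observed by staff (Section 5.5), so this adds at most one data field on six days.
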